6 STUDY ASSESSMENTS

6.1 Efficacy Assessments

6.1.1 CT Scan of Abdomen (CT Subset of Subjects Only)

Subjects with standard of care CT scans (with or without contrast) that include the abdomen conducted at admission (within 48 hours of first hospital arrival and up to 24 hours after first IP dose) will have a follow-up CT scan (without contrast) of the abdomen (conducted per institutional guidelines) at the timepoint specified in the Schedule of Assessments if the subject is still in the hospital. The purpose is to assess changes in muscle volumes in a standardized way. When available, follow-up standard of care CT scans (with or without contrast) including the abdomen may be used if collected at the timepoint specified in the Schedule of Assessments.

Subjects that do not have a CT scan (with or without contrast) including the abdomen conducted as standard of care upon admission (within 48 hours of first hospital arrival and up to 24 hours after first IP dose) will not have a follow-up CT scan conducted or collected for the study and will not be a part of the CT subset.

For subjects in the CT Subset, the admission and follow-up CT scans of the abdomen will be collected and uploaded for central interpretation per the study specific Imaging Acquisition Manual.

6.1.2 Sit-to-Stand Assessment

Trained site personnel will conduct the sit-to-stand physical assessment per the study-specific Functional Assessments Manual.

The number of sit-to-stand maneuvers a subject completes over a period of 30 seconds will be recorded.

6.1.3 Organ Dysfunction Time to Recovery (TTR)

Organ dysfunction time to recovery (TTR) will be assessed based on the criteria presented in Appendix 4: Organ Dysfunction TTR. The definition of time to recovery is the first day meeting the organ failure recovery criteria in cardiovascular, hematologic, hepatic, renal, and respiratory systems without any subsequent days with further organ system failure.

6.1.4 Sequential Organ Failure Assessment Score (SOFA)

The Sequential Organ Failure Assessment (SOFA) is a scoring system that assesses the performance of several organ systems in the body (e.g., neurologic, blood, liver, kidney, and blood pressure/hemodynamics) and assigns a score based on the data obtained in each category (see Appendix 5: SOFA Criteria).

The SOFA score will be calculated using 6 common points of data:

• Respirations (partial pressure of arterial oxygen [PaO₂] and FiO₂)

Confidential Page 32 of 64

- Coagulation (platelets)
- Liver (bilirubin)
- Cardiovascular (hypotension)
- Central nervous system (Glasgow Coma Score [GCS])
- Renal (creatinine or urine output)

The full-length SOFA score ranges from 0 to 24. Worst values of the day should be used to calculate SOFA score. See the Study Reference Manual for details.

6.1.5 Chelsea Critical Care Physical Assessment (CPAx)

Trained site personnel will conduct the Chelsea Critical Care Physical Assessment (CPAx) per the study-specific Functional Assessments Manual. The CPAx is designed to measure functional recovery from critical illness. The CPAx includes the following 10 components:

- Respiratory function
- Cough
- Moving within bed
- Supine to sitting on the edge of bed
- Dynamic sitting
- Standing balance
- Sit to stand
- Transferring from bed to chair
- Stepping
- Grip strength

The CPAx components will be graded on a 6-point scale from dependent to independent (0 to 5). The individual values will be collated giving a total score out of 50.

6.1.6 Medical Research Council Sum Score (MRC-SS)

Trained site personnel will conduct the Medical Research Council Sum Score (MRC-SS) physical assessment per the study-specific Functional Assessments Manual.

The MRC-SS measures global peripheral muscle strength which ranges from 0 (complete paralysis) to 60 (normal strength). The MRC-SS includes 6 muscle strength tests:

- Shoulder abduction
- Elbow flexion
- Wrist extension
- Hip flexion
- Knee extension
- Ankle dorsiflexion

Confidential Page 33 of 64

6.1.7 Barthel Index

The Barthel Index will be administered by asking the subject, friends/relatives/caregivers, and/or nurses/doctors about the subject's performance either in person or via telephone. Use direct observation if obtainable, but direct testing is not required for administration. Each subject's performance should be established using the best available evidence (see Study Reference Manual).

The Barthel Index is an ordinal scale used to measure performance of activities of daily living (ADL) (see Appendix 6: Barthel Index). It uses 10 variables describing ADL and mobility:

- Presence or absence of fecal incontinence
- Presence or absence of urinary incontinence
- Help needed with grooming
- Help needed with toilet use
- Help needed with feeding
- Help needed with transfers (e.g., from chair to bed)
- Help needed with walking
- Help needed with dressing
- Help needed with climbing stairs
- Help needed with bathing

Each performance variable is rated on a scale with a given number of points assigned to each level or ranking. Scores range from 0 to 100 with a higher number associated with a greater likelihood of being able to live at home with a degree of independences following discharge from the hospital.

6.1.8 Medical Outcomes Study Questionnaire Short Form 36v2 (SF-36v2) Health Survey

Each subject will complete the Short Form 36v2 (SF-36v2) Health Survey by self-reporting electronically (e.g., using smartphone or tablet).

The SF-36v2 Health Survey is an indicator of overall health status. The SF-36v2 Health Survey uses 8 scaled scores and the scores will be weighted sums of the questions in each of the following sections:

- Vitality
- Physical functioning
- Bodily pain
- General health perceptions
- Physical role functioning
- Emotional role functioning
- Social role functioning
- Mental health

Confidential Page 34 of 64

Scores range from 0 to 100 with lower scores indicating more disability and higher scores indicating less disability.

6.1.9 Time of Extubation

Time of intubation(s) and successful extubation(s) will be recorded. Extubation will be considered successful if subject remains extubated for at least 24 hours.

6.1.10 Occurrence of Sepsis

Time and occurrence of sepsis and septic shock will be recorded. Sepsis is defined as an acute change in total SOFA score ≥2 points consequent to infection. Septic shock is defined as sepsis with persisting hypotension requiring vasopressors to maintain Mean Arterial Pressure ≥65 mmHg.

6.1.11 Discharge and Disposition

Time of hospital discharge and disposition type (e.g., step-down unit, rehabilitation facility, home) will be recorded. Time of hospital discharge will be defined as the date the subject is cleared for discharge from the hospital.

6.1.12 General Health Inquiry

A general health inquiry, including documentation of any new significant medical diagnoses and/or hospitalizations, will be conducted by telephone.

6.1.13 Overall Survival

Confirmation of survival status will be obtained by speaking directly with subject, via medical records, or public health records.

6.1.14 Research Blood Samples (US Sites Only)

Research blood samples will be collected from subjects and shipped to a central laboratory, stored, and batched for analysis. Research samples will be stored no longer than 2 years after the completion of the study and include:

- Leukocyte Gene Expression: gene expression analysis for blood leukocyte gene transcription changes in response to trauma
- Plasma PK: pharmacokinetic analysis measuring the concentration of FDY-5301 in plasma
- Blood Biomarkers: analysis of metabolic, inflammatory, and biochemical markers of muscle damage in blood

Confidential Page 35 of 64

6.2 Demographics and Safety Assessments

6.2.1 Demographics

Demographic information, including gender, birth date, race, and ethnicity will be recorded following consent.

6.2.2 Medical History

Significant historic and current medical conditions or illnesses, allergies to medications, and prior surgical interventions will be recorded.

6.2.3 Physical Examination

Physical examinations will be performed per institutional guidelines.

6.2.4 Estimated Height and Weight

Height and weight will be recorded. Estimated values are acceptable per institutional guidelines.

6.2.5 Serum Pregnancy Test

A serum pregnancy test will be performed only for female subjects of reproductive potential. A woman is considered of reproductive potential following menarche and until becoming postmenopausal unless permanently sterile (i.e., both ovaries have been removed, fallopian ducts tied, womb removed, or completed menopause).

6.2.6 Concomitant Medications

For all medications ongoing at time of consent (prescription, nonprescription, and supplements), the medication name, dose, route, frequency, start and stop dates, and indication will be recorded in the subject's medical record and in the CRF. Imaging contrast agents and any parenteral or enteral feeding, including amount of energy and protein, will also be recorded.

6.2.7 Safety Laboratory Tests

Clinical laboratory evaluations will be performed by each site's clinical laboratory per institutional guidelines. See Appendix 2: Clinical Laboratory Tests for a list of required analytes. Additional assessments may be performed between scheduled study visits as clinically required to diagnose and monitor AEs/SAEs.

6.2.8 12-Lead Electrocardiogram

Standard 12-lead ECGs will be performed as single recordings and read at the clinical site.

Confidential Page 36 of 64

6.2.9 Trauma Related Injury Severity Score (TRISS)

A Trauma Related Injury Severity Score (TRISS) will be recorded (see Appendix 3: TRISS Method). See the Study Reference Manual for details.

The TRISS is a scoring system that assesses probability of survival by looking at the following:

- Injury Severity Score (ISS) looks at head and neck, face, chest, abdomen and pelvic contents, extremity and pelvic girdle, and external injuries and each body region is given a score based on the Abbreviated Injury Score Code (AIS)
- Revised Trauma Score (RTS) also looks at Systolic blood pressure (SBP), Respiratory rate (RR), and GCS
- Age

Confidential Page 37 of 64

7 STUDY TREATMENTS

7.1 Description of Investigational Product

FDY-5301 is sodium iodide (chemical formula NaI) administered as an isotonic solution for intravenous injection with a concentration of 7.2 mg/mL. The dosage form of FDY-5301 is a small-volume parenteral solution. The solution has a pH between 7.0 and 9.5. Normal saline will be used as placebo.

7.2 Randomization, Stratification and Blinding

Study treatment will consist of FDY-5301 or placebo.

All subjects who fulfill all study eligibility criteria will be randomized to receive one of the treatment kits allocated by a computer-generated randomization code (FDY-5301 at 1 mg/kg, or 2 mg/kg, or volume-matched placebo). Randomization will be stratified by whether the subject has pelvic or lower limb fractures.

The clinical trial site will remain blinded to treatment allocation of active or placebo, as placebo and active vials will be identical in appearance.

7.3 Procedure for Unblinding

The randomization code may be broken by the Investigator to manage an urgent medical event provided that knowledge of the IP (i.e., active or placebo) will alter the subject's management. If possible, the Medical Monitor should be contacted to discuss the case before the code is broken.

For each subject, the treatment group can be unblinded using the interactive response technology (IRT) system and the site's Emergency Unblinding Code, provided with the site's study start-up materials. Using the Emergency Unblinding Code, the Investigator or designee will be able to unblind a subject by following instructions on the IRT Quick Reference Guide.

Unblinding must be clearly justified and explained in source documentation, along with the date on which the code was broken and identity of the person who authorized unblinding.

7.4 Prohibited Concomitant Medications

The following medications and supplements are prohibited until Day 28 as they may confound efficacy and safety measures in the study:

- High-dose Selenium (>55µg per day)
- High-dose vitamins or nutritional supplements (> recommended daily allowance)
- Use of any investigational drug or device that may confound efficacy or safety measures in this study

Confidential Page 38 of 64

8 INVESTIGATIONAL PRODUCT MATERIALS AND MANAGEMENT

8.1 Investigational Product

FDY-5301 is delivered as a single dose, non-preserved liquid parenteral solubilized in water for injection and balanced with sodium chloride. Each vial is formulated to contain 20 mL of a 7.2 mg/mL concentration of sodium iodide to support clinical dosing by IV injection.

Placebo is delivered as a single dose, non-preserved liquid parenteral consisting of a formulation matched compendial saline. Each vial is formulated to contain 20 mL of saline to support clinical dosing by IV injection.

8.2 Packaging and Labeling

IP will be manufactured, packaged, and labeled by contract manufacturing organizations on behalf of the Sponsor in accordance with Good Manufacturing Practice.

IP will be supplied in cartons containing 7 kits. One carton will be assigned to a single subject upon randomization. A single kit within that carton will be used each day for the assigned subject's daily dose. Each kit will contain 2 x 20 mL vials to ensure sufficient dose volume for anyone with a body weight of \leq 140 kg (or \leq 309 lbs).

Refer to the Study Pharmacy Manual for details of the packaging and description of the label.

8.3 Shipment and Storage

IP will be shipped to sites following the completion of study initiation and receipt of IEC/IRB approval. IP will be stored as supplied (20°C to 25°C) in a secured location at the clinical trial site. IP should not be stored frozen and direct exposure to sunlight and heat should be avoided. If storage conditions are found to be outside of the specified storage requirements, immediately contact the sponsor. Contact details are provided in the Study Pharmacy Manual.

8.4 Preparation and Administration

The formulation has no preservative and is intended for single use only. Injection solutions will be prepared using aseptic technique and inspected prior to administration. The solution for injection is a clear, colorless solution with no particulate matter.

Preparation of the administered dose will be achieved by adjusting the volume of undiluted solution (calculation is based on IP concentration of 7.2 mg/mL) according to treatment assignment. Dosage is based on the subject's body weight (estimated or actual) at screening.

IP will be administered intravenously by a healthcare professional by bolus injection over no more than 10 minutes. Use of an infusion pump is acceptable provided it can administer the total volume in less than 10 minutes. IP may be administered through a central line as long as the line is flushed prior to and following injection. IP must be administered without mixing with any other IV drugs.

Confidential Page 39 of 64

The first IP administration must occur as soon as possible and within 48 hours of first hospital arrival time (i.e. in case of transfers, use time of arrival to first hospital immediately post injury) and then daily for up to 7 days at approximately the same time each day (±4 hours using the time of day of the first IP administration).

8.5 Investigational Product Accountability and Disposal

IP will only be used for purposes of this study. The clinical site staff will be responsible for IP accountability, reconciliation, and record maintenance in accordance with all applicable regulatory requirements.

An IP accountability record must be kept current and will contain an accurate and current accounting of study drug receipt, storage, administration, and destruction.

At the end of the study, any remaining IP will be disposed of as per Sponsor instructions (e.g., at the site by using approved drug destruction methods) and a final IP reconciliation statement must be completed and provided to the Sponsor.

Accountability records must be made available to the study monitor for verification throughout the course of the study.

Confidential Page 40 of 64

9 SAFETY: ADVERSE EVENTS

9.1 Definitions

An adverse event (AE) is defined as any untoward medical occurrence in a patient or clinical investigation subject administered an investigational product (pharmaceutical) and which does not necessarily have a causal relationship with the treatment. An AE can therefore be any unfavorable and unintended sign (including an abnormal laboratory finding), symptom, or disease temporally associated with the use of a medicinal (investigational) product, whether or not related to the investigational product. A relationship to the investigational product is not necessarily proven or implied.

All adverse events occurring from the time of consent until Day 28, observed by the Investigator or reported by the subject (whether or not attributed to IP), will be recorded. The following attributes must be recorded in subject's medical records and in the CRF: description, start and stop dates, seriousness, outcome, severity, relationship to IP, and action taken with IP.

Any medical condition already present at the time of consent should not be reported as an AE unless the medical condition (or signs or symptoms) present at consent changes in severity or seriousness at any time during the study. In this case, it should be reported as an AE.

9.2 Recording Diagnosis Versus Signs and Symptoms

Wherever possible, a specific disease or syndrome rather than individual associated signs and symptoms should be identified by the Investigator and recorded in the CRF. However, if an observed or reported sign or symptom is not considered a component of a specific disease or syndrome by the Investigator, it should be recorded as a separate AE in the CRF. Additionally, a condition that leads to a medical or surgical procedure should be recorded as an AE rather than the procedure (e.g. record appendicitis instead of appendectomy).

9.3 Laboratory Abnormalities or Other Abnormal Assessments

The following laboratory or other assessment abnormalities will be considered AEs and recorded in the subject's medical record and in the CRF:

- Any result deemed clinically significant by the Investigator and that is not part of another reported clinical diagnosis
- Any result leading to discontinuation or interruption of IP
- Any result that requires therapeutic intervention or a change in subject management

Abnormalities that do not meet one of the above conditions will not be recorded on the CRF.

9.4 Relationship to Investigational Product

The Investigator will classify every AE according to its relationship to IP. Investigators should pay particular attention to etiology of subject's symptoms that are anticipated in the ICU setting.

The relationship categories are listed in Table 3.

Confidential Page 41 of 64

Table 3: Relationship of Adverse Events to IP

Classification	Definition		
Related	The AE follows a reasonable temporal sequence from administration of IP and cannot readily have been produced by the subject's clinical state, other modes of therapy, or concomitant medications administered to the subject		
Not Related	The AE is clearly related to other factors, such as the subject's clinical state, other modes of therapy, or concomitant medications administered to the subject		

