9.6 Reporting Serious Adverse Events

A serious adverse event (SAE) is any untoward medical occurrence that at any dose:

- Results in death
- Is life-threatening (NOTE: The term "life-threatening" in the definition of "serious" refers to an event/reaction in which the subject was at risk of death at the time of the event/reaction; it does not refer to an event/reaction which hypothetically might have caused death if it were more severe)
- Requires inpatient hospitalization or results in prolongation of existing hospitalization

Confidential Page 42 of 64

NOTE: Prolongation of existing hospitalizations for social or situational reasons will not be considered an SAE (e.g., waiting for placement or availability in a step-down unit or rehabilitation facility, no place to stay, etc.).

- Results in persistent or significant disability/incapacity
- Is a congenital anomaly/birth defect
- Is a medically important event or reaction

Medical and scientific judgment should be exercised in deciding whether reporting is appropriate in other situations, such as important medical events that may not be immediately life threatening or result in death or hospitalization but may jeopardize the subject or may require medical or surgical intervention to prevent one of the other outcomes listed in the above definition. These should also usually be considered serious. Examples of such medical events include cancer, allergic bronchospasm requiring intensive treatment in an emergency room or at home, blood dyscrasias or convulsions that do not result in hospitalizations, or the development of drug dependency or drug abuse.

Initial Reports

All SAEs occurring from the time of informed consent until Day 28, regardless of causality or relationship to treatment, must be reported to Medpace Clinical Safety within 24 hours of the knowledge of the occurrence. After Day 28, any SAE that the Investigator considers related to IP must be reported to Medpace Clinical Safety or the Sponsor/designee.

To report the SAE, the Investigator/designee completes the SAE form electronically in the electronic data capture (EDC) system for the study. When the form is completed, Medpace Safety personnel will be notified electronically by the EDC system and will retrieve the form.

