9.8 Expedited Reporting Requirements

9.8.1 Suspected Unexpected Serious Adverse Reaction

A suspected unexpected serious adverse reaction (SUSAR) is considered any SAE for which there is a reasonable possibility that the IP caused the SAE and is considered "unexpected" i.e., not listed in the Reference Safety Information section of the Investigator's Brochure, or is not listed at the specificity or severity that has been observed in an adverse reaction, the nature or severity of which is not consistent with the applicable product information.

The Sponsor or designee will report all relevant information about fatal or life-threatening SUSARs or IND safety reports (INDSRs) as soon as possible to the FDA and applicable competent authorities, and in any case no later than 7 calendar days after knowledge by the Sponsor or designee of such a case. Relevant follow-up information will subsequently be communicated as soon as the information is available but no later than 15 calendar days after the Sponsor or designee receives the information.

All other SUSARs or INDSRs will be reported to the FDA and applicable competent authorities as soon as possible but within a maximum of 15 days of first knowledge by the Sponsor or designee. The Sponsor or designee will also inform all Investigators of SUSARs or INDSRs as required.

Confidential Page 45 of 64

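### The two adverse-event causality categories in Table 3 are not exhaustive, and the bar for Related is stricter than the reasonable-possibility standard in section 9.8.1

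*Combined protocol and SAP*

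**What the plan says.** Protocol section 9.4 states that "The Investigator will classify every AE according to its relationship to IP". Table 3 offers two categories.

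- **Related**: the timing after dosing is reasonable, and the event "cannot readily have been produced by the subject's clinical state", other treatment or concomitant drugs. Both conditions must hold.
- **Not Related**: "The AE is clearly related to other factors, such as the subject's clinical state", other treatment or concomitant drugs.

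The only further guidance in the section is that "Investigators should pay particular attention to etiology of subject's symptoms that are anticipated in the ICU setting". There is no intermediate category, and no rule for an event that could be explained either way.

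Section 9.8.1 uses a different test. A SUSAR is drawn from "any SAE for which there is a reasonable possibility that the IP caused the SAE". That section does not refer to Table 3.

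The classification is used in two stated places. Section 10.2.3 tabulates AEs, TEAEs and SAEs by treatment group, severity and relationship to study drug. Section 9.6 makes it a reporting condition late in follow-up: "After Day 28, any SAE that the Investigator considers related to IP must be reported".

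**The concern.** A forced two-way choice works only if the two definitions between them cover every event. Here each definition sets its own demanding condition, and the space between them is unassigned.

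That space matters in this population. Section 4.1 enrols patients with hemorrhagic shock who are expected to be ventilated for at least a day, and section 1.2.4 describes them as at high risk of organ failure. Events that could come from the injury, its treatment or the study drug are to be expected, and these are the events the table does not place.

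The use of a lower causality threshold in section 9.8.1 adds a second problem. The same SAE could fail Related on the case report form and still satisfy the causality part of the SUSAR definition, and the protocol does not say how the two judgements are to be reconciled.

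At stake are the meaning of the tables by relationship, the consistency of the investigator's opinion as an input to SUSAR assessment, and the trigger for reporting SAEs after Day 28.

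**Working it through.** The documents give no figure on this point and no arithmetic applies. The check is logical: list every combination of the two things Table 3 asks about and see which category the wording assigns.

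Inputs, all from Table 3 in section 9.4:

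- timing relative to study drug: reasonable, or not reasonable (2 levels);
- alternative cause: could not readily explain the event; could readily explain it but is not clearly the cause; is clearly the cause (3 levels).

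This gives 2 × 3 = 6 combinations.

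| Timing | Alternative cause | Meets Related? | Meets Not Related? | Category |
|---|---|---|---|---|
| Reasonable | Could not readily explain | Yes | No | Related |
| Reasonable | Could readily, not clearly | No | No | None |
| Reasonable | Clearly the cause | No | Yes | Not Related |
| Not reasonable | Could not readily explain | No | No | None |
| Not reasonable | Could readily, not clearly | No | No | None |
| Not reasonable | Clearly the cause | No | Yes | Not Related |

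Related covers 1 combination, Not Related covers 2, and 6 − 1 − 2 = 3 have no category. These are counts of logical cases. They say nothing about how often each case will occur.

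The second row is the important one. The event fails Related because the clinical state could readily have produced it, and fails Not Related because that cause is not clear. It follows that a genuine drug effect resembling a common ICU complication cannot satisfy Related as written.

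Now set the two standards side by side for that same row. Section 9.8.1 asks whether there is a reasonable possibility that the drug caused the event. Plausible timing with an alternative cause that is not clearly responsible can leave such a possibility open. Table 3 does not allow Related for that event. So Table 3 is the stricter of the two.

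Finally, trace what depends on the classification:

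- AE recording to Day 28 (section 9.1): does not depend on attribution.
- SAE reporting to Day 28 (section 9.6): does not depend on attribution.
- Event summaries by randomized group (section 10.2.3): do not depend on attribution.
- Event summaries by relationship (section 10.2.3): depend on it directly.
- Investigator opinion as an input to SUSAR assessment (section 9.8.1): affected.
- SAE reporting after Day 28 (section 9.6): depends on it directly.

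**The case against.** The strongest reply is that little of the safety evaluation rests on Table 3. All AEs and SAEs to Day 28 reach the database whatever their attribution, the trial has a placebo group, and an independent committee monitors safety (section 11.1). The comparison of event rates between groups is untouched. This stands, and it limits the point to attribution and late reporting.

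A second reply is that section 9.8.1 governs expedited reporting by the sponsor or its designee. Since every SAE to Day 28 reaches the safety group, the reasonable-possibility test can be applied whatever the site has ticked. This also stands: no lost SUSAR is shown for that window. What remains is that the investigator's opinion is formed under a different and stricter rule.

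A third reply is that exposure after Day 28 is small. At most 7 daily doses are given (section 8.4), the half-life is 6 to 8 hours (section 1.5), and Day 28 falls 28 − 7 = 21 days after a Day 7 dose. Telephone contacts at Months 3 and 6 still collect new diagnoses, hospitalizations and survival (Table 1, sections 6.1.12 and 6.1.13). This reduces the likely number of affected events. It does not replace SAE reporting, for which the investigator's relatedness call remains the condition.

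A reader might go further and infer that drug-related harms will be under-counted, or that Related is almost unreachable. The documents do not support that. The wording excludes events the clinical state could readily explain, not every event it could conceivably explain. An investigator who takes the Not Related definition literally could equally place an ambiguous event in Related. The direction is a risk; it is not a demonstrated result.

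A reader might also infer that the signals named in the protocol would be missed. Thyroid function is measured on schedule and analysed through group means and outliers (section 10.2.3, Appendix 2), with no relatedness call. The small excess of nonsustained ventricular tachycardia at 2 mg/kg in the earlier STEMI trial (section 1.2.3) is a between-group observation, which Table 3 does not touch.

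**Conclusion.** The point holds as a defect in a stated rule. Table 3 requires a classification for every event but leaves 3 of 6 logical combinations without one, including the plausible-timing, ambiguous-cause event that matters most in this setting. Its threshold for Related is stricter than the causality standard in section 9.8.1, and no text in the protocol reconciles them.

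The consequence is inconsistent classification of ambiguous events, with a risk of under-attribution to study drug. It is confined to the AE, TEAE and SAE summaries by relationship, the investigator's input to SUSAR assessment, and SAE reporting after Day 28. Its size cannot be estimated, because the documents do not say how many events will be ambiguous or how investigators will resolve them.

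The conclusion assumes that investigators apply Table 3 as worded and that no site manual or training material outside the protocol supplies a rule for ambiguous events.

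**What to change.** Reconcile Table 3 with section 9.8.1, using the protocol's own standard:

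- **Related**: there is a reasonable possibility that study drug caused the event.
- **Not Related**: there is no reasonable possibility that study drug caused the event.

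Because the second is the negation of the first, every event has a category. Add one sentence stating that an alternative explanation on its own does not rule out Related, and that timing and alternative causes are both weighed in judging whether the possibility is reasonable. A blanket rule sending every event with two possible causes to Related is not needed: it would go beyond section 9.8.1 and could make the tables by relationship less informative.

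The cost is a change to the wording of Table 3, site retraining, more events classed as related, and more causality review. Data collection, endpoints and sample size are unaffected.
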